#### 6.2. Key Definitions

#### 6.2.1. Baseline

Unless otherwise stated, the baseline value for any variable will be the last non-missing value taken prior to the receipt of study treatment at the Baseline visit (Day 1). The receipt of study treatment is defined as the 1st injection of study drug if it exists. Otherwise, baseline is defined as the last value taken prior to the randomization.

For diary data (CCI), the baseline values will be derived from data collected during the 7 days prior to the first administration of study drug, if it exists. Otherwise, the data collected during 7 days prior to randomization will be used. Baseline score will be the weekly prorated average of non-missing subject diary scores reported during the 7 days. A minimum of 4 daily scores out of the 7 days is required to calculate the weekly prorated average score.

#### **6.2.2.** Study Day

Study Day is the number of days since the first dose date. If the assessment date is after the randomization, the study day is calculated as (date of assessment - first dose date + 1). If the assessment date is prior to the first dose date, the study day is calculated as (date of assessment - first dose date).

#### 6.2.3. Study period

First treatment date is defined as the date of 1st study drug (Nemolizumab or Placebo) injection.

Last treatment date is defined as the date of last study drug (Nemolizumab or Placebo) injection.

Treatment period is defined as follow:

- Subject completed the treatment: first dose date up to Week 16
- Subject who discontinued the treatment: first dose date up to earliest among:

- o 4 weeks after the last study drug administration
- o the early study termination date if available

Screening period is defined the period before the treatment period.

Follow-up period is defined the period after the treatment period.

## 6.3. Missing Data

Adverse events and concomitant medications with missing assessment times will have imputed times for the purposes of assessing treatment emergence for AEs or classifying medications into prior/concomitant. However, the assessment times (start date, stop date) without imputation will be presented in the listings.

For the start of a concomitant medication or AE:

- Only the year is reported: If the subject received the first study drug dose in the year reported, then the date of the first dose of study drug will be used as the start date; otherwise, January 1 of the year reported will be used as the start date.
- The month and year are reported: If the subject received the first study drug in the month and year reported, then the date of the first dose of study drug will be used as the start date; otherwise, the first day of the month and year will be used as the start date.
- The time is missing: If the start date is the same as the date the subject started receiving study drug, then the time of the first dose of study drug will be used as the start time; otherwise, 00:00 will be used as the start time.

For the end of a concomitant medication or AE:

- Only the year is reported: The earlier between December 31 of the year reported and the date of the last study contact with the subject will be used as the stop date.
- The month and year are reported: The earlier between the last date of the month and year reported and the date of the final contact with the subject will be used as the stop date.

If an AE has the start date completely missing and the stop date on/after the first dose date of study drug, this AE will be considered as treatment emergent.

If a medication has the stop date completely missing and ongoing tick box in CRF is checked, this medication will be considered as concomitant.

Imputations or calculations for specific efficacy endpoints will be included in the section that describes the analysis of that endpoint.

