9.6.1.1 Topical Background Therapy

At the screening visit (≥ 14 days prior to baseline), subjects who are using a stable regimen of medium- or low-potency TCS therapy, with or without TCI therapy, should continue their therapy regimen.

Background therapy use should be adjusted to the disease activity and tolerability of the subject, including tapering when signs and symptoms improve, discontinuation when lesions clear, and restarting if signs and symptoms recur, at the discretion of the investigator.

Subjects who are not using a stable regimen of topical therapy at the screening visit should not use topical background therapy during the study, unless required as rescue therapy (see Section [9.6.1.3](#)).

Subjects with a history of intolerance to TCS or for whom TCS are not advisable (eg, hypersensitivity, significant skin atrophy) must not use TCS background therapy.

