## 6.6. Subgroups

Subgroup analysis will be performed in an exploratory manner to investigate the treatment effect across various subgroup. The following subgroup analyses will be performed for the primary and secondary vaccine response endpoints:

- By age (<18 years; >=18 years)
- By sex (Male, Female)
- By race (White, Black or African American, Asian, Other)
- CCI
- Baseline Weight (≤Q1, <Q1 median, <median Q3, > Q3)
- Baseline Weight (≤90 kg, > 90 kg)
- Coronavirus disease-19 (COVID-19) Infection (Subjects infected by COVID-19, Subjects not infected)
- Background therapy (subjects with background therapy, subject without background therapy)

In addition, analyses will be performed on the last subgroup (background therapy) for selected secondary efficacy endpoints.

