#### 7.6. Medications/Therapies

Prior medications/therapies are defined as medications/therapies which stop before 1st injection of study drug. Concomitant medications/therapies are defined as medications/therapies which start or stop on or after the 1st injection of study drug.

If start and/or stop dates of medications and therapies are missing or partial, the dates will be compared as far as possible with the date of first dose of study drug. Medications and therapies will be assumed to be Concomitant, unless there is clear evidence (through comparison of partial dates) to suggest that they started and stopped prior to the first dose of study treatment. If there is clear evidence to suggest that the medication or medical and surgical procedure started and stopped prior to the first dose of study drug, they will be assumed to be Prior.

For prior and concomitant medications, incomplete (i.e., partial missing) start dates and/or stop dates will be imputed using the algorithm described in Section 6.3.

Medications will be coded using the World Health Organization's Drug Dictionary (WHO DD) Version Global B3 SEP 2019 using the Preferred Anatomical Therapeutic Chemical (ATC) terms. TCI and TCS will be automatically identified using the following rule:

- TCS will be identified by ATC code "D07A".
- TCI will be identified by ATC code "D11AH" and with standardized medication name "TACROLIMUS" and "PIMECROLIMUS".

Prior and Concomitant medications will be summarized separately by Anatomical Therapeutic Chemical (ATC) level 2, level 4, and preferred name in frequency tables using ITT, mITT and safety population. Subjects with more than one medication in a given ATC level and preferred name will be counted only once in that category. It will be sorted in descending frequency of ATC level and of PT within ATC level term.

The following summaries will be produced:

- Prior medication
- Concomitant medication
- Rescue medication during treatment period (ITT Population only)
- Rescue medication during follow-up period (ITT Population only)

Sponsor: Galderma S.A./Galderma R&D, LLC; Protocol No.: RD.06.SPR.118380 V4.0, 06Jul2022

 Background therapy (ITT Population only) consisting of TCS and TCI with start date prior to study drug administration and that are not classified as rescue therapy

All medications will be listed. The background TCS dispensation/receipt will also be listed.

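### Read as written, the SAP's partial-date rule can remove true pre-study TCS/TCI users from the background-therapy flag when the start is known only to the year (rarely, the month) of first dosing

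*SAP*

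**What the plan says.** Four pieces of text bear on this.

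- **Imputation (SAP 6.3).** For a start known only to the year: "If the subject received the first study drug dose in the year reported, then the date of the first dose of study drug will be" the imputed start. For a start known to the month and year: "If the subject received the first study drug in the month and year reported, then the date of the first dose of study drug" is used in the same way. Otherwise the first day of the reported year or month is used. The section opens by giving the purpose as "imputed times for the purposes of assessing treatment emergence for AEs or classifying medications into prior/concomitant".
- **Application to medications (SAP 7.6).** For prior and concomitant medications, "incomplete (i.e., partial missing) start dates and/or stop dates will be imputed using the algorithm described in Section 6.3".
- **Background therapy (SAP 7.6).** The summary table entry is described as "consisting of TCS and TCI with start date prior to study drug administration and that are not classified as rescue therapy".
- **Subgroup (SAP 6.6).** The list for the primary and secondary vaccine response endpoints includes "Background therapy (subjects with background therapy, subject without background therapy"). The same split is used for selected secondary efficacy endpoints. No definition is given there and 7.6 is not cited.

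Protocol 9.6.1.1 identifies background users by their status at screening, at least 14 days before baseline: "subjects who are using a stable regimen of medium- or low-potency TCS therapy, with or without TCI therapy, should continue their therapy regimen".

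**The concern.** Moving an unknown start to the first-dose date is the cautious choice for adverse events, because it errs towards calling them treatment-emergent. For the prior/concomitant label of a continuing topical it does no harm: under SAP 7.6 anything that stops on or after the first injection is concomitant wherever its start is placed.

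The background flag asks the opposite question, namely whether the product was in use before study drug. Here the imputed date is the one that fails the test. It is also an implausible date for these records. Protocol 9.6.1.1 and Table 3 (9.6.2) do not allow subjects without a stable regimen to begin TCS or TCI from Day 1 except as rescue, and the flag already leaves rescue out. A non-rescue topical with an ambiguous start is therefore more likely to be existing therapy than a Day 1 start.

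The resulting error runs one way, from users to non-users. It would undercount background use in Table 14.1.4.3.3 and mix users into the group without background therapy, which blurs the contrast the subgroup is meant to show.

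**Working it through.** The plan gives no figure to reproduce, so the check is to apply the rules as written.

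**Rules.** Let D be the first-dose date and S the start date after imputation.

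- Year only (6.3): if the reported year is the year of D, S = D; otherwise S = 1 January of that year.
- Month and year (6.3): if both match D, S = D; otherwise S = the first of that month.
- Background (7.6): S < D, and not rescue.

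When S = D the condition S < D fails. The missing-time rule does not rescue it: "If the start date is the same as the date the subject started receiving study drug, then the time of the first dose" is used, which gives a tie with dosing, not an earlier time.

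**Illustrative dates** (invented, first dose 20 Sep 2022):

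| True start | Recorded as | Imputed start | Background? |
|---|---|---|---|
| 10 Feb 2022 | 10 Feb 2022 | 10 Feb 2022 | yes |
| 10 Feb 2022 | Feb 2022 | 1 Feb 2022 | yes |
| 10 Feb 2022 | 2022 | 20 Sep 2022 | **no** |
| 3 Sep 2022 | Sep 2022 | 20 Sep 2022 | **no** |
| 3 Sep 2022 | 2022 | 20 Sep 2022 | **no** |
| 1 May 2021 | 2021 | 1 Jan 2021 | yes |

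A less precise record of the same fact changes the classification.

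**How often each branch acts, given a partial date.** Assume first-dose days spread evenly over a calendar year and true starts spread evenly from 14 days to L days before first dose. The 14 days come from Protocol 9.6.1.1; L is an assumption. The share of records that lose background status is:

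| L (days) | Year-only record | Month-only record |
|---|---|---|
| 90 | 86% | 6.1% |
| 182 | 73% | 2.8% |
| 365 | 48% | 1.3% |
| 730 | 24% | 0.7% |

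The month branch is narrow because a start at least 14 days before D can fall in the same month only if D is on day 15 or later. In a 365-day year that is 7×17 + 4×16 + 14 = 197 days, and 197/365 = 54%. Even then the topical must have begun earlier in that month.

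**From record to subject.** A subject changes subgroup only if no other non-rescue TCS/TCI record has a start before D. A user of both TCS and TCI with one usable date stays in the group with background therapy.

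These shares are conditional on a partial date. The documents give neither the frequency of partial dates nor the proportion of background users.

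**The case against.** The strongest reply is that the chain is inferred. SAP 6.3 states two purposes and a background flag is neither. In 7.6 the cross-reference to 6.3 follows the prior/concomitant rules, while the background wording comes later as an entry in a list of summaries. SAP 6.6 does not cite 7.6, and SAP section 9, where the subgroup is used again, is not visible. A separate background record may exist: Protocol Appendix 4 names background topical therapy apart from concomitant therapies for remote collection, and 7.6 lists TCS dispensation.

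This stands as a limit on certainty. It does not remove the point. SAP 7.6 imputes medication dates without repeating the 6.3 purposes, in the section holding the only visible definition. If the narrower reading is the intended one, the SAP states no rule for deciding whether a partial start precedes study drug for this flag, and a sentence is needed anyway.

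Three further replies also stand in part.

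- Subjects must have had AD for at least 2 years, so many starts may lie in an earlier calendar year, where the rule works correctly.
- Nothing suggests that partial dates for pre-baseline topicals differ by randomised arm, so there is no evident bias between arms within a subgroup.
- Data queries or the blind data review (Protocol section 16) could settle individual cases, though neither is stated as the rule for this flag.

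**Conclusion.** The point holds as a defect in the derivation as written, small in consequence. A stable pre-screening topical dated only to the year of first dosing, or rarely only to the month, fails the 7.6 definition. A subject with no other qualifying record is then classed as without background therapy and missed in Table 14.1.4.3.3. This rests on 7.6 being the operative definition for 6.6 and on the 6.3 algorithm feeding it.

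A reader might infer more, and the documents do not support it:

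- *That every user with a partial date is misclassified.* Earlier-year dates, most month-only dates and subjects with a second qualifying record are classified correctly.
- *That a definite share of the subgroup is contaminated.* If half of 245 subjects were users (about 123) and 5–15% of them had a start that flips, 6 to 18 would move, making up 6/(123+6) = 4.7% to 18/(123+18) = 12.8% of the group without background therapy. Both inputs are assumptions with no source in the documents, so the number affected cannot be computed.
- *That the main result is at risk.* SAP 6.6 calls the subgroup analyses exploratory, and the primary mITT analysis does not use the flag.

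**What to change.** In SAP 7.6, state that the 6.3 start-date imputation does not apply to the background-therapy flag. Classify a non-rescue TCS/TCI whose partial start could be before first dose as background therapy, using the use status documented at screening where it is recorded, unless the record shows a start on or after first dose. Have 6.6 cite this definition. Keep 6.3 unchanged for AE emergence and prior/concomitant classification.

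The cost is a short SAP addition and one derivation change. It can run on the recorded partial dates alone, so it needs no new data; whether a screening status item exists cannot be seen. The downside is that a non-rescue topical actually started after dosing, with only the year recorded, could be counted as background therapy. That should be rare, since rescue records are excluded and new non-rescue TCS/TCI use is prohibited for subjects not on stable therapy.

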13.1 Adverse Events

Adverse Event Definition

An AE is defined as any untoward medical occurrence in a clinical study subject administered a medicinal product which does not necessarily have a causal relationship with this treatment. An AE can therefore be any unfavorable and unintended sign (including an abnormal laboratory finding), symptom, or disease temporally associated with the use of a medicinal (investigational) product, whether or not it is related to the medicinal (investigational) product. This includes an exacerbation of preexisting conditions or events, intercurrent illnesses, drug interaction, or the significant worsening of the indication under investigation that is not recorded elsewhere in the eCRF under specific efficacy assessments.

Note(s):

- Any new sign or symptom reported by the subject that appears after accidental or intentional overdose or misuse should be reported as an AE.
- Whenever possible, a diagnosis should be reported on the AE form, instead of signs, symptoms, or abnormal laboratory values.
- Pregnancy is not to be considered an AE; however, it must be monitored and reported as described in Section 13.1.5.
- Each worsening of a chronic disease from the screening visit should be reported as a new AE.

The investigator or designee will report all AEs that occur from the time the ICF is signed until the end of the study. The sponsor/CRO should be informed if the investigator becomes aware of any safety information that appears to be drug-related, even after the subject has completed the clinical study.

This document is confidential.

Page 78 of 133

At each post enrollment visit, the investigator (or sub-investigator) will question the subject about AEs using an open non persuasive question to elicit reporting of AEs (for example, “Have you noticed any change in your health since the last visit?”). Directed questioning and examination will then be performed as appropriate.

Any AE occurring during the AE reporting period, whether it is related to the study drug(s) or not, will be recorded immediately in the source document and described on the Adverse Event Form (“AE Form”) along with the date of onset, severity, relationship to the study drug(s), and outcome, without omitting any requested and known information. Additional information will be requested under certain circumstances.

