16.6 Safety Analysis

All safety analyses will be conducted on the SAF, by treatment group.

All reported AEs will be coded using the Medical Dictionary for Regulatory Activities (MedDRA), version 22.0 or later. The treatment-emergent period will be defined as the period of time from the first dose date of study treatment through 12 weeks (84 days) after the last dose of study treatment (ie, up to the follow-up visit for completers), or the date of rollover to the LTE study (SPR.118163), whichever is earlier. The incidence of TEAEs (events with onset dates on or after the start of the study drug), drug-related TEAEs, SAEs, TEAEs leading to study drug discontinuation and treatment-emergent AESIs will be included in incidence tables, summarized by System Organ Class (SOC) and Preferred Term (PT). Events with missing onset dates (and no data to suggest the

[figure not shown]
This document is confidential.

event stopped prior to study treatment start) will be included as treatment-emergent. The incidence of TEAEs by severity, counting multiple AEs under SOC and PT for a subject at the maximum severity will be presented. All AEs will be listed by subject, along with information regarding onset, duration, relationship and severity to study drug, action taken with study drug, treatment of event, and outcome.

Clinical laboratory data and vital signs will be summarized using descriptive statistics, including observed values and change from baseline values, as well as numbers of subjects with values outside limits of the normal range, including shifts from baseline at each time point.

Summary tables will be provided for 12-Lead ECG, Physical Examination (Full and Symptom-oriented), ACT, PEF, and Respiratory Exam, by treatment group and visit where appropriate. Listings will also be provided.

[figure not shown]
CCI

This document is confidential.

Page 106 of 133

CCI

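### SAP 6.3 moves partial AE start dates to first dose without checking the stop date, so AEs that ended before dosing can be counted as TEAEs; it also leaves ongoing AEs with unknown onset without a rule

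*SAP*

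**What the plan says.** SAP 10.3 defines a TEAE by onset on or after the first dose date and sends partly missing dates to SAP 6.3. There, AEs with incomplete dates "will have imputed times for the purposes of assessing treatment emergence for AEs", so this section sets the TEAE flag.

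For partial start dates it has two rules:

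- Month and year known: "If the subject received the first study drug in the month and year reported, then the date of the first dose of study drug" is used as the start.
- Year only: "If the subject received the first study drug dose in the year reported, then the date of the first dose of study drug" is used as the start.

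If the reported month or year does not match, the first day of that month or year is used. Neither rule refers to the stop date. Partial stop dates are set to the end of the reported month or year, capped at the last contact.

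For a completely missing start, SAP 6.3 says: "If an AE has the start date completely missing and the stop date on/after the first dose date of study drug, this AE" counts as treatment-emergent. It has a rule for ongoing records ("If a medication has the stop date completely missing and ongoing tick box in CRF is checked"), but for medications only.

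Protocol 16.6 defines a TEAE by onset on or after the start of study drug. An event with a missing onset date, where nothing suggests that the "event stopped prior to study treatment start) will be included as treatment-emergent". SAP 14, which lists changes from the protocol, does not mention this point.

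Pre-dose events are in the database. Under Protocol 13.1, "The investigator or designee will report all AEs that occur from the time the ICF is signed until the end of the study", and screening lasts 2 to 4 weeks (Protocol 7.1).

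**The concern.** An event that stopped before first dose cannot have started on or after it. A rule that ignores a recorded stop date can therefore produce a record whose onset is later than its resolution and whose TEAE flag is wrong under either document's definition. This does not depend on whether the missing onset dates in Protocol 16.6 include partly missing ones.

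The second point is about coverage. An AE with unknown onset that is still ongoing has no stop date to compare with first dose. The protocol has a default for it and the SAP does not repeat that default, so the classification is left to whoever programs the flag.

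At stake is the flag behind the TEAE tables in SAP 10.3: overall, related, serious, by severity, and leading to discontinuation. A few records matter little for common events but can be visible for rare ones.

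**Working it through.** The plan gives no figure to reproduce. The check applies the written rules to test records.

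**Assumed dates (not in the documents):** first dose 20 Mar 2022, last contact 4 Sep 2022.

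| Record | Start | Stop | SAP 6.3 start | SAP flag | Protocol 16.6 |
|---|---|---|---|---|---|
| A | Mar 2022 | 10 Mar 2022 | 20 Mar 2022 | TEAE | not TEAE |
| B | 2022 | 25 Feb 2022 | 20 Mar 2022 | TEAE | not TEAE |
| B2 | 2022 | Feb 2022 (imputed 28 Feb) | 20 Mar 2022 | TEAE | not TEAE |
| C | missing | ongoing | none | no rule | TEAE |
| D | missing | 10 Mar 2022 | none | not TEAE | not TEAE |
| E | missing | 1 Apr 2022 | none | TEAE | TEAE |
| F | missing | Mar 2022 (imputed 31 Mar) | none | TEAE | TEAE |
| G | Mar 2022 | ongoing | 20 Mar 2022 | TEAE | TEAE |
| H | Feb 2022 | ongoing | 1 Feb 2022 | not TEAE | not TEAE |

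A, B and B2 show the stated rule giving a wrong flag. In A the imputed start is 20 − 10 = 10 days after the recorded stop. C shows the gap: no SAP sentence classifies it. D to H agree.

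**How often could it happen?** The rule goes wrong only if three things hold together: the start is partial, its month (or year) matches that of first dose, and the stop is before first dose. The documents give no frequency for the first, so the number of affected records cannot be computed. The other two can be illustrated for month-and-year starts. Assumptions: first dose uniform over a calendar year, onset uniform over screening, and every AE stopping 7 days after onset.

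| | 14-day screening | 28-day screening |
|---|---|---|
| Onset in first-dose month | 75% | 52% |
| Onset in first-dose month and stopped before dosing | 32% | 31% |
| Stopped before dosing | 7/14 = 50% | 21/28 = 75% |
| In first-dose month, among those stopped | 0.319/0.50 = 64% | 0.306/0.75 = 41% |

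So under these assumptions about a third of screening AEs with an unknown start day would be misflagged. For year-only starts the year matches in about 98% (14-day) to 96% (28-day) of cases, so there the stop date decides almost alone.

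**Size per record.** With about 123 subjects per arm, one subject wrongly counted as having a given event moves that arm's incidence by 1/123 = 0.8 percentage points.

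**The case against.** The strongest case on the other side has five parts.

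- **Missing onset.** A reader might infer that the SAP drops ongoing AEs with unknown onset and so contradicts the protocol. The text does not support that. SAP 6.3 gives a sufficient condition (if a stop date on or after first dose exists, the AE counts); it does not say only if. Protocol 16.6 covers the ongoing case, and SAP 14 does not withdraw it. This objection stands: the point is an uncovered case.
- **Frequency.** A reader might take the 75% and 52% to mean that most screening AEs with an unknown day become TEAEs even when resolved. Those are shares of screening days in the dosing month and ignore whether the event had stopped. With that condition the illustration gives about a third. Sites must also record onset and resolution dates (Protocol 13.1) and data management resolves queries (Protocol 17.2), so few partial dates should remain. This stands.
- **Direction.** Counting too many events is the cautious error for safety, and the rule is the same in both blinded arms. No bias against nemolizumab is shown. This stands, although symmetry does not make an impossible onset date acceptable.
- **Visibility.** All AEs, SAEs and AESIs are listed by subject (SAP 10.3), with dates shown unimputed (SAP 6.3). No event vanishes; only the summary flag is affected. This stands.
- **AESI tables.** Protocol 13.1.1 and 13.1.4 restrict AESI to events after first dose, so a resolved screening event has little route into them. This stands.

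None of these answers the missing stop-date check. The SAP already uses such a check for medications: SAP 7.6 classes them as concomitant unless partial dates clearly show that they started and stopped before first dose. AEs have no counterpart.

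**Conclusion.** The point holds in two parts of unequal weight.

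1. The partial-start rule in SAP 6.3 is wrong as written. It can class an AE recorded as ended before dosing as a TEAE, with onset after resolution, contrary to SAP 10.3 and Protocol 16.6. This follows from the text and needs no assumption about frequency.
2. The rule for a completely missing start does not carry over the protocol's default for ongoing AEs or AEs with no stop date. This is an omission to close, not evidence that such events will be excluded.

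The number of affected records is unknown and probably small, and both arms are treated alike. The 0.8 points per misclassified subject assumes that close to the planned 123 per arm are in the safety population. The one-third illustration rests on the assumed 7-day duration and uniform dates, and applies only to screening AEs whose start day is unknown. It is worth correcting before the TEAE flag is final because the correction is simple, not because a large effect is expected.

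**What to change.** Replace the AE start-date rules in SAP 6.3 with text along these lines:

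> Stop dates are imputed first, to the latest date consistent with the reported parts. A partial AE start that matches the month or year of first dose is set to the first-dose date, unless the recorded or imputed stop is before first dose. In that case the earliest date consistent with the reported parts is used and the AE is not treatment-emergent. An AE whose start is completely missing is treatment-emergent unless its recorded or imputed stop is before first dose; ongoing AEs and AEs with no stop date are included (Protocol 16.6).

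The order matters. If partial stop dates were not imputed before the check, an AE with start Mar 2022 and stop Mar 2022 could be read as not shown to reach first dose and would be lost. With the stop imputed first (31 Mar), it stays a TEAE, as it is now. Applied to the test records, the text changes A, B and B2 to not TEAE, makes C a TEAE, and leaves D to H as they are.

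The cost is a short SAP edit and one change to the AE derivation. No new data are needed. If the sponsor prefers to keep the current rule, SAP 14 should say so and give the reason.
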